3 OBJECTIVES AND ENDPOINTS

OBJECTIVES	ENDPOINTS	JUSTIFICATION FOR ENDPOINTS
Primary		
To determine the effect of omega-3 polyunsaturated fatty acids (PUFA) treatment on blood biomarkers of neuronal injury and blood biomarkers of inflammation and a blood biomarker of neurogenesis	Neurofilament light chain [NFL], Neurogranin [NRGN] and Intercellular adhesion molecule 5 [ICAM5], high sensitivity C-reactive protein [CRP], IL-6, IL-10, and brain derived neurotrophic factor [BDNF]	If omega-3 fatty acid supplementation decreases the levels of biomarkers of neuronal injury and inflammation and increases the levels of biomarkers of neurogenesis, then there is a strong likelihood it will improve clinical outcome
Secondary		

 1. To demonstrate the feasibility of enrolling, treating and conducting follow-up assessments on mTBI patients presenting to the University of Michigan 2. To acquire preliminary data on the effect of omega-3 PUFA treatment on delayed functional recovery, moderate/severe post-concussive symptoms and cognitive impairment. 3. To acquire preliminary data on the types and incidence of serious adverse events (SAEs) in the Omega-3 PUFA treatment arm compared to the placebo arm 	
 1. Successful enrollment of 50 subjects within 1 year 2. Measurement of functional recovery using the Glasgow Outcome Scale Extended (GOSE), measurement of symptomatic recovery using the Rivermead Post-concussive symptoms questionnaire (RPQ) and cognitive impairment using a neurocognitive battery of tests 3. Measurement of the incidents of gastrointestinal distress and clinically significant bleeding 	These endpoints will help inform the design of a multi-center phase II trial

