4 STUDY DESIGN

4.1 OVERALL DESIGN

We hypothesize that treatment of traumatic brain injury patients with omega-3 fatty acids will result in a decrease in blood concentrations of biomarkers of neuronal injury and inflammation and an increase in the blood concentration of biomarkers of neurogenesis. This is a randomized, placebo-controlled, double-blinded pilot phase II clinical trial. Participants will be randomized either a single dose of 6g of DHA+EPA for 1 month followed by 1.2g/day of DHA+EPA for two additional months or to placebo treatment for 3 months. Blood samples will be drawn at enrollment, 2 weeks, 1 month and 3 months post-injury. Biomarkers of neuronal injury, inflammation, and neurogenesis will be measured in batches. Functional and symptomatic recovery will be assessed at 2 weeks, 1 month and 3 months. Additionally, cognitive impairment will be assessed at 3 months.

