6.1.2 DOSING AND ADMINISTRATION

Every attempt will be made to start treatment as soon as possible after enrollment. The first dose will be administered within 7 days of injury. The intervention group will receive 6g per day of DHA+EPA for 1 month followed by 1.2 g/day of EPA+DHA for two additional months. The control group will receive placebo treatment for 3 months.

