9 STATISTICAL CONSIDERATIONS

9.1 STATISTICAL HYPOTHESES

- Primary Efficacy Endpoint(s):

Omega-3 fatty acid supplementation results in a decrease in the area under the concentration versus time curve for neurofilament light chain, CRP, IL-6 and IL-10 during the 3 months following TBI and an increase in the area under the concentration curve for brain derived neurotrophic factor.

- Secondary Efficacy Endpoint(s):

Omega-3 fatty acid supplementation improves functional outcome, post-concussive symptoms and cognitive decline post-TBI

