9.2 SAMPLE SIZE DETERMINATION

This is a pilot study of 50 patients.

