9.3 STATISTICAL ANALYSES

9.4.1 GENERAL APPROACH

We will examine blood levels of biomarkers of omega-3 intake, axonal injury, and inflammation (red blood cell and plasma omega-3 index, NFL, ICAM5, CRP, IL-6 and IL-10) at baseline and at 3 months in both the intervention and the control groups and test the hypothesis that omega-3 PUFA treatment increases omega-3 PUFA blood levels and decreases levels of biomarkers of axonal injury and inflammation. To examine the effect of omega-3 PUFA treatment on biomarkers of neuronal injury and inflammation, we will construct multiple linear regression models with generalized estimating equations (GEE) and robust variance estimation to account for correlations within repeated measurements. This will allow us to determine whether variations in the levels of NFL, ICAM5, CRP, IL-6 and IL-10 over the 3 month study period differ among those receiving omega-3 PUFA supplementation versus those receiving placebo.

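### Section 9.1 states the primary hypothesis as an AUC difference, but the GEE in 9.4.1 names no AUC contrast and no enrolment-level covariate

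*Combined protocol and SAP*

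**What the plan says.** Section 9.1 hypothesises "a decrease in the area under the concentration versus time curve for neurofilament light chain, CRP, IL-6 and IL-10" over the 3 months after injury, and a rise in the same quantity for BDNF.

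Section 9.4.1 (under 9.3) has two parts. It first examines biomarker levels "at baseline and at 3 months in both the intervention and the control groups". It then proposes "multiple linear regression models with generalized estimating equations (GEE) and robust variance estimation to account for correlations within repeated measurements", in order to learn "whether variations in the levels of NFL, ICAM5, CRP, IL-6 and IL-10 over the 3 month study period differ" between arms. It does not mention AUC. It gives no time coding, arm-by-time term, contrast, outcome scale or covariate, and it does not list BDNF. ANCOVA appears only in the abbreviation list (10.2).

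The enrolment value is already collected. Section 4.1 says: "Blood samples will be drawn at enrollment, 2 weeks, 1 month and 3 months post-injury". The schedule of activities (1.3) shows the same draws. Section 9.2 gives the size without a derivation: "This is a pilot study of 50 patients".

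**The concern.** The primary objective in section 3 is "To determine the effect of omega-3 polyunsaturated fatty acids (PUFA) treatment on blood biomarkers of neuronal injury" and on the inflammation and neurogenesis markers. Section 9.1 makes this precise by choosing the AUC. Section 9.4.1 then leaves several analyses open, including a linear arm-by-time slope, a change from enrolment to 3 months, a 3-month level and a weighted average over visits. These are different quantities, and they can disagree even in direction. With the contrast, the covariate and the scale all open, the choice can be made after the data are seen.

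Precision is also at stake. With 50 patients, an analysis that ignores an enrolment level already measured will often have a wider confidence interval than it needs.

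**Working it through.** The plan has no figure to reproduce, because 9.2 gives no alpha, power, effect or SD.

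**Inputs from the documents:** 50 patients (9.2); samples at enrolment, 2 weeks, 1 month and 3 months (4.1, 1.3); eligibility up to 7 days after injury (5.1).

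**Assumed:** 25 per arm (the allocation ratio is not stated), complete data, equal SDs at all visits, and correlation r from 0.2 to 0.8 between enrolment and follow-up.

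**1. Different contrasts test different things.** Take nominal days 0, 14, 30, 90. The trapezoid weights are 14/2 = 7, (14+16)/2 = 15, (16+60)/2 = 38 and 60/2 = 30. Suppose treatment lowers the level by d at 2 weeks and 1 month and the arms are equal again at 3 months.
- AUC difference: −(15+38)d = −53d.
- Change to 3 months: 0.
- Linear slope: the mean day is 33.5 and the sum of squared deviations is 1122.25+380.25+12.25+3192.25 = 4707. The slope is (−d)(−19.5−3.5)/4707 = +23d/4707 per day, the opposite sign to the AUC.

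Suppose instead that the effect is a constant 0.5 SD at all three follow-up visits. Simulation (4,000 runs per setting, exchangeable r = 0.2 / 0.5 / 0.7, uncorrected sandwich variance with t reference) gave power of:
- linear slope: 15 / 25 / 36%
- visit average weighted 15:38:30, unadjusted: 71 / 58 / 50%
- the same average, adjusted for enrolment level: 74 / 78 / 88%

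**2. One model can serve both sections.** AUC = 7·Y0 + 15·Y1 + 38·Y2 + 30·Y3. Once Y0 is a covariate, the 7·Y0 term is absorbed. With complete data on common days, and an enrolment slope at each visit, 15, 38 and 30 times the visit differences sum to exactly the arm coefficient from regressing AUC on arm and enrolment level.

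**3. Variance, unadjusted over adjusted for enrolment level.**
- Change: 2(1−r)/(1−r²) = 2/(1+r).
- 3-month level: 1/(1−r²).
- AUC: w'Rw / (w'Rw − (R0·w)²), with w = (7, 15, 38, 30), R the correlation matrix and R0 its first row. Exchangeable example at r = 0.4: w'Rw = 0.6×2618 + 0.4×8100 = 4810.8; R0·w = 7 + 0.4×83 = 40.2; ratio = 4810.8/(4810.8 − 1616.04) = 1.51.

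| Unadjusted contrast | r = 0.2 | 0.4 | 0.6 | 0.8 |
|---|---|---|---|---|
| Change to 3 months | 1.67 | 1.43 | 1.25 | 1.11 |
| 3-month level | 1.04 | 1.19 | 1.56 | 2.78 |
| AUC, exchangeable | 1.18 | 1.51 | 2.20 | 4.33 |
| AUC, exchangeable, enrolment at day 7 | 1.13 | 1.42 | 2.05 | 3.99 |
| AUC, correlation r, r², r³ by visit | 1.04 | 1.11 | 1.32 | 2.07 |

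Divide each ratio by 1 + 1/(50−4) = 1.022 for the cost of estimating the enrolment slope.

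**4. Where adjustment does not help.** When enrolment and outcome are nearly uncorrelated, a level or AUC analysis pays the 2% for almost nothing. Against a change score, with k the follow-up SD over the baseline SD, the ratio is (k²+1−2rk)/(k²(1−r²)), which equals 1 when rk = 1. At k = 1.4 and r = 0.7 it is (1.96+1−1.96)/(1.96×0.51) = 1.0004, or 0.979 after the slope cost.

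**5. Illustrative power, raw AUC to baseline-adjusted AUC** (log-normal, log SD 0.8, 40% reduction at every follow-up visit, 25 per arm). Exchangeable: 65 to 79% at r = 0.4 and 55 to 83% at r = 0.6. Decaying: about 69 to 73% and about 59 to 70%.

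**The case against.** The strongest reply is that 9.4.1 commits to no unadjusted contrast. A multiple regression can include the enrolment level, and the sentence on baseline and 3 months describes what will be examined, not the GEE terms. A reader might infer that the plan has chosen an inefficient change-from-baseline analysis. The documents do not support that, and each ratio above compares the proposal with a reading the plan permits, not one it states. Keeping the enrolment value as a repeated outcome, with a common mean across arms and a suitable working correlation, would also recover much of the same information.

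A reader might also infer that naming the AUC is itself a free gain in precision. It is not; the covariate supplies the gain. The gain may be small: enrolment is an acute sample and the last visit is at 3 months, so decaying correlation is at least as plausible as exchangeable.

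The weights 15:38:30 are nominal. Enrolment can fall up to 7 days after injury, and with varying days the identity in step 2 is only approximate (off by about 2% of the effect in a simulation). The documents do not compel the raw scale either. In the same log-normal illustration with exchangeable correlation, a log-scale adjusted contrast had 90 / 94% power at r = 0.4 / 0.6, against 79 / 83% raw, but it estimates a different quantity.

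All of this limits the size of the claim. The mismatch between 9.1 and 9.4.1 remains.

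**Conclusion.** The point holds as a specification gap with an inexpensive remedy. Section 9.1 names an AUC hypothesis. Section 9.4.1 does not say how the GEE tests it and does not say that the enrolment level is a covariate.

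The benefit of adjustment rests on assumed correlations, equal SDs, complete data and equal allocation. Under these, unadjusted AUC has 1.18 to 4.33 times the adjusted variance (exchangeable) or 1.04 to 2.07 times (decaying), before the 2% cost. The loss is at most about 2% in variance, when enrolment and outcome are nearly uncorrelated or, against a change score, when r times the SD ratio is near 1.

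It would be wrong to conclude that the trial misses a promised power. This is a pilot, 9.2 promises none, and every power figure here is illustrative. Adjustment is also safe only if the enrolment sample precedes treatment. Section 6.1.2 implies this order ("Every attempt will be made to start treatment as soon as possible after enrollment") but does not state it.

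**What to change.** In 9.4.1, for each biomarker in the 9.1 hypothesis, including BDNF:

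- Model the 2-week, 1-month and 3-month levels by GEE with arm, visit, arm-by-visit, enrolment level and enrolment level-by-visit.
- Name the baseline-adjusted AUC contrast of the visit differences as the primary test, with trapezoid weights from the scheduled days (nominally 15:38:30), and state the AUC time origin.
- Fix the outcome scale, raw or log, before unblinding; the other can be a sensitivity analysis.
- Confirm that the enrolment sample is drawn before the first dose.
- Optionally, use a small-sample-corrected sandwich variance (for example Mancl-DeRouen) with a t reference. This is minor: the uncorrected z-test of one contrast has a size of about 6.1% with normal data, and a correction of this kind (HC3) cost about 3 points of power in the raw-AUC illustration.

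The cost is wording only. A participant without an enrolment sample drops out of the model. One who misses a follow-up visit still contributes, as the planned GEE already allows, but unweighted GEE is generally valid only if missingness is unrelated to the outcomes. The change settles the contrast within each biomarker. It does not settle multiplicity across the five, or the role of ICAM5 (in 9.4.1 but not 9.1) and neurogranin (a primary endpoint in section 3, absent from both).

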7 STUDY INTERVENTION DISCONTINUATION AND PARTICIPANT DISCONTINUATION/WITHDRAWAL

7.1 DISCONTINUATION OF STUDY INTERVENTION

Discontinuation from taking the study medication does not mean discontinuation from the study, and remaining study procedures should be completed as indicated by the study protocol. If a clinically significant finding is identified (including, but not limited to changes from baseline) after enrollment, the investigator or qualified designee will determine if any change in participant management is needed. Any new clinically relevant finding will be reported as an adverse event (AE).

The data to be collected at the time of study intervention discontinuation will include the following:

- Blood samples, functional, symptomatic and cognitive outcomes data

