7.2 PARTICIPANT DISCONTINUATION/WITHDRAWAL FROM THE STUDY

Participants are free to withdraw from participation in the study at any time upon request.

An investigator may discontinue or withdraw a participant from the study for the following reasons:

- Pregnancy (self-reported)
- Significant study intervention non-compliance
- If any clinical adverse event (AE), laboratory abnormality, or other medical condition or situation occurs such that continued participation in the study would not be in the best interest of the participant
- Disease progression which requires discontinuation of the study intervention
- If the participant meets an exclusion criterion (either newly developed or not previously recognized) that precludes further study participation
- Participant unable to receive the study medication for 2 weeks or more

The reason for participant discontinuation or withdrawal from the study will be recorded on the Case Report Form (CRF). Subjects who sign the informed consent form and are randomized but do not receive the study intervention may be replaced. Subjects who sign the informed consent form, and are randomized and receive the study intervention, and subsequently withdraw, or are withdrawn or discontinued from the study, will be replaced.

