7.3 LOST TO FOLLOW-UP

A participant will be considered lost to follow-up if he or she fails to return for a scheduled visit and is unable to be contacted by the study site staff.

The following actions must be taken if a participant fails to return to the clinic for a required study visit:

- The site will attempt to contact the participant and reschedule the missed visit within 2 weeks and counsel the participant on the importance of maintaining the assigned visit schedule and ascertain if the participant wishes to and/or should continue in the study.
- Before a participant is deemed lost to follow-up, the investigator or designee will make every effort to regain contact with the participant (where possible, 3 telephone calls and, if necessary, a certified letter to the participant's last known mailing address or local equivalent methods). These contact attempts should be documented in the participant's medical record or study file.
- Should the participant continue to be unreachable, he or she will be considered to have withdrawn from the study with a primary reason of lost to follow-up.

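### The biomarker GEE names no small-sample correction, reference distribution or working correlation; in its standard form at 50 participants its error bars are modestly too small

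*Combined protocol and SAP*

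**What the plan says.** The only model given for the biomarkers is in section 9.3, under General Approach: "multiple linear regression models with generalized estimating equations (GEE) and robust variance estimation to account for correlations within repeated measurements". Its stated purpose is to find whether biomarker levels "over the 3 month study period differ among those receiving omega-3 PUFA supplementation versus those receiving placebo". The text stops there. It does not name a working correlation, a finite-sample adjustment to the variance, the distribution used for tests and intervals, or an assumption about missing visits.

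The surrounding facts are these:
- Section 9.2: "This is a pilot study of 50 patients". No alpha, power, effect size or dropout rate is given.
- Section 4.1: "Blood samples will be drawn at enrollment, 2 weeks, 1 month and 3 months post-injury", so there are four repeated values per participant.
- Section 7.2 lets the investigator withdraw a participant for reasons that include adverse events, laboratory abnormalities and "Significant study intervention non-compliance". Treated participants who leave, "and subsequently withdraw, or are withdrawn or discontinued from the study, will be replaced".
- Section 7.3: a participant who cannot be reached is one for whom "he or she will be considered to have withdrawn from the study with a primary reason of lost to follow-up".
- Section 7.1, on the other side: "Discontinuation from taking the study medication does not mean discontinuation from the study".

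**The concern.** Two properties of GEE matter here.

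First, the robust (sandwich) variance is justified by a large number of independent clusters. The clusters are participants, about 25 per arm. The estimator uses fitted residuals, which are smaller on average than the true errors. The usual software default also refers the result to a z or chi-square distribution, as if the variance were known. Both push the same way: intervals too short, and too many rejections when there is no effect. The shortfall grows with the number of contrasts tested jointly and with the number of covariates.

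Second, unweighted GEE on the visits that happen to be available is guaranteed valid in general only when dropout is completely at random. Withdrawal for adverse events or non-compliance can be related to arm and to the participant's earlier course, so that condition is not assured.

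At stake is the comparison of the biomarkers, which are the primary endpoints.

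**Working it through.** **Inputs.** From the documents: 50 participants, 4 samples each, linear GEE with robust variance. Assumed, because the documents do not say: 1:1 allocation (m = 25 per arm; 20 and 17 per arm stand for attrition), two-sided 5%, outcome SD 1, Normal data unless stated. The plan states no standard error, error rate or power for this model, so there is no figure of its own to reproduce.

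**Step 1. Single contrast, complete data, closed form.** With m per arm, the ratio of uncorrected sandwich SE to unbiased SE is √((m−1)/m). The true size of the z-test is 2·P(t on 2m−2 df > 1.96·√((m−1)/m)).

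| m per arm | SE ratio | Effective cut-off | True size |
|---|---|---|---|
| 25 | √(24/25) = 0.980 | 1.920 on 48 df | 6.1% |
| 20 | √(19/20) = 0.975 | 1.910 on 38 df | 6.4% |
| 17 | √(16/17) = 0.970 | 1.901 on 32 df | 6.6% |

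**Step 2. Treatment-by-visit test, 3 df, complete data, closed form.** With a saturated visit model and equal arms, the uncorrected Wald statistic is Hotelling's T² times m/(m−1). It is compared with the chi-square value 7.815. The equivalent F cut-off is 7.815·((m−1)/m)·(2m−4)/(3(2m−2)) on 3 and 2m−4 df.

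- m = 25: 7.815 × 0.96 × 46/144 = 2.397 on 3 and 46 df, true size 8.0%.
- m = 20: 7.815 × 0.95 × 36/114 = 2.344 on 3 and 36 df, true size 8.9%.

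These sizes do not depend on the within-person correlation. A simulation of 20,000 trials gave 8.0% and 9.0%. A separate run of 3,000 trials per setting, with exchangeable working correlation, gave 8.4% and 9.3% (Monte Carlo SE about 0.5 points). In that run a corrected variance with an F reference gave 5.2-5.3%.

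**Step 3. Single contrasts with covariates and random dropout, simulated.** 25 per arm, AR(1) correlation 0.6, no effect, 4,000 runs (Monte Carlo SE √(0.05 × 0.95/4000) = 0.34 points). Each cell gives change from enrollment / 3-month difference.

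| Setting | SE ratio, uncorrected | Size, z | Size, Mancl-DeRouen with t(48) |
|---|---|---|---|
| Complete, no covariates | 0.97 / 0.97 | 6.0% / 6.0% | 4.5% / 4.5% |
| Complete, 4 covariates | 0.98 / 0.95 | 6.2% / 7.4% | 4.7% / 4.4% |
| 20% dropout, 4 covariates | 0.95 / 0.93 | 6.8% / 7.4% | 4.7% / 4.4% |
| 30% dropout, 4 covariates | 0.95 / 0.93 | 7.1% / 7.4% | 5.0% / 4.2% |

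With strongly skewed raw-scale values the SE ratio fell to 0.87-0.92, but the size was only 5.1-6.0%.

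**Step 4. Dropout missing at random, deliberately adverse.** Dropout depends on the previous observed value, in opposite directions by arm. About 28% are missing at 3 months and the true 3-month difference is 0. There were 2,000 runs at n = 50 and 150 at n = 1000.

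| Working correlation | Bias, n = 50 | Bias, n = 1000 | Size at n = 50, z | Size at n = 50, corrected |
|---|---|---|---|---|
| Independence | −0.275 SD | −0.272 SD | 15.6% | 12.3% |
| Exchangeable | +0.023 SD | +0.033 SD | 5.9% | 4.1% |
| Unstructured | −0.037 SD | −0.023 SD | 9.5% | 7.1% |

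A second calculation, with about 22% missing at 3 months and 400 trials per correlation structure, gave 0.25-0.27 SD under independence, 0.01-0.05 SD under exchangeable, and about 0 with a likelihood model. The bias under independence does not shrink with sample size, and the variance correction does not cure it.

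**The case against.** Several stronger readings are tempting, and the documents do not support them.

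- *The plan chose an uncorrected variance.* It did not say so. The phrase on robust variance neither includes nor excludes a correction. The figures describe the standard form of the named method, which is what an analyst following the text would most likely run.
- *The trial's 5% level is broken.* No alpha is stated anywhere. The 5% is a convention brought in to measure the shortfall.
- *The error rate is 8-9%.* That applies to a 3-df treatment-by-visit test, one fair reading of section 9.3. The hypotheses in section 9.1 concern area under the curve, a single contrast per marker, for which about 6% is the relevant figure. In a pilot, one point of excess changes little.
- *GEE requires completely random dropout, so the result will be biased.* This is too absolute. In Step 4 the bias is large under independence and close to zero under a working correlation near the truth. The dropout rate and mechanism are assumed. Samples are assayed in batches (section 4.1) and the study team is blinded (section 6.3), so dropout driven directly by a biomarker value is unlikely; it would have to act through a correlate such as symptoms. Follow-up after stopping medication, repeated contact attempts and visit payments also limit dropout.
- *GEE must be replaced.* The error-rate argument does not lead there, because a corrected GEE restores a size near 5%.

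All of these limits stand. It does not follow that the point is only a missing detail. The named method in its usual form gives intervals that are too short at this sample size before any dropout occurs, and the dropout result turns on a setting left open.

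**Conclusion.** The point holds, with modest size: as written, the method gives error bars that are too small unless the analyst adds something the text does not mention. For a single contrast with complete data and no covariates, standard errors are about 2-3% too small and the true size is about 6%. With dropout and covariates the shortfall reaches about 7% and the size about 7.4%. A 3-df treatment-by-visit test has a size of about 8-9%. These figures rest on 1:1 allocation, a two-sided 5% level, Normal data and an uncorrected sandwich with a z or chi-square reference.

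The dropout part is conditional. Under one assumed adverse missing-at-random mechanism, the spurious 3-month difference is about 0.27 SD with independence and 0.05 SD or less with exchangeable. This shows that the working correlation must be fixed in advance; it does not predict what this trial will see.

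**What to change.** Amend section 9.3 before unblinding, in one of two equally acceptable ways.

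1. Keep GEE, and specify a small-sample corrected variance (for example Mancl-DeRouen), a t or F reference with stated degrees of freedom, a non-independence working correlation, and adjustment for the enrollment biomarker value. Exchangeable behaved well in Step 4. Unstructured did less well at n = 50 (7.1% even after correction).
2. Use a likelihood mixed model for repeated measures with Kenward-Roger degrees of freedom, which is valid under missing at random.

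In either case, name the contrast to be tested, state the missing-data assumption, and add one sensitivity analysis to departures from it, since withdrawal for adverse events or non-compliance may violate missing at random as well.

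The cost is analysis wording and a standard procedure call; no participants, visits or assays are added. Intervals become wider. From Step 3, for the 3-month contrast, corrected GEE widens them by (1.006/0.966) × (2.011/1.960) = 1.07, about 7%, with complete data and no covariates. With 30% dropout and four covariates the factor is (1.028/0.929) × (2.011/1.960) = 1.14, about 14%. The mixed model also relies on an assumed covariance structure.
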